8.4.3 Loss of confidentiality

A risk of taking part in this study is the possibility of a loss of confidentiality or privacy. Loss of confidentiality or privacy means having personal information shared with someone who is not on the study team and was not supposed to see or know about your information. All study data will be stored in password protected computers or file cabinets in locked offices. All research team members will pass the protection of human subjects and research HIPAA exams and sign a protocol-specific conflict of interest. All procedures have been designed to protect each participant's privacy and allow for anonymous participation. All study data will be maintained in a completely secure and HIPAA compliant environment. All CUIMC servers have HIPAA compliant security

8.5 Social Impact Events

Individuals enrolled in this study may experience personal problems resulting from the study participation. Such problems are termed social impact events. Although study sites will make every effort to protect participant privacy and confidentiality, it is possible that participants' involvement in the study could become known to others, and that participants may experience stigmatization or discrimination as a result of being perceived as being HIV infected or at risk for HIV infection. For example, participants could be treated unfairly, or could have problems being accepted by their families and/or communities. Problems may also occur in circumstances in which study participation is not disclosed, such as impact on employment related to time taken for study visits.

In the event that a participant reports a social impact event, every effort will be made by study staff to provide appropriate assistance, and/or referrals to appropriate resources. Social impact events are documented and reviewed on a scheduled basis by the protocol team leadership with the goal of reducing their incidence and enhancing the ability of study staff to mitigate them when possible.

Social impact events that are judged by the MPIs/designee to be serious, unexpected, or more severe or frequent than anticipated, will be reported to the responsible site's Ethics Committee/Institutional Review Board (EC/IRB) promptly, or otherwise in accordance with the EC/IRB's requirements.

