7.3.4 Data Safety and Monitoring Board

The contact Principal Investigator (PI) will enlist a Data and Safety Monitoring Board (DSMB) to oversee the data, safety elements, and overall integrity of the study. The DSMB will: 1) monitor recruitment, enrollment, and adherence of study participants; 2) formulate criteria for modifying or discontinuing the intervention of individual subjects; and 3) review serious adverse events (SAEs). The objectives of the DSMB will be to assess the safety of the intervention trial and to assure the highest degree of subject safety. We will work with the NIMH to identify individuals to serve in this role. Monitoring board membership will be reviewed and approved by NIMH. Should there be any questions regarding the independence of the monitoring board it will be addressed and corrected if necessary.

The biostatistician with clinical trials expertise and the data manager will prepare monitoring reports in advance of every DSMB meeting. The DSMB will remain blinded to randomization status unless, for safety reasons, the DSMB, in consultation with the NIMH Program Administrator, decides it is important to unmask the data.

The DSMB will: 1) review the protocol as funded and make suggestions for any changes (especially safety related); 2) assess the endpoints suggested by the investigators; 3) review study progress by reviewing recruitment, retention, and compliance of participants and data quality; 4) determine formatting for data reports; 5) review endpoints for safety; 6) submit written reports and

suggestions to the team; and 7) add to or modify this list of objectives. The Project Director will document the minutes of the meetings and distribute to the Chair of the DSMB for final approval or revision.

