7.4.2 Adverse event reporting

We will follow the guidelines that require investigators to promptly notify the IRB (within days of the occurrence) when SAEs occur. SAEs will be defined as death, life threatening illness, hospitalization or prolongation of hospitalization, and persistent/significant disability. The IRB requires that any SAE that is unexpected and related or possibly related to the research intervention must be reported. SAEs that are unrelated to the research intervention do not have to be reported to the IRB (however, we will report these to the monitoring entity and NIH). Risks that are described in the protocol and consent form do not have to be reported as SAEs unless

the expected SAE occurs more frequently or is more serious than expected. One exception to this rule is in the case of a death. All deaths must be reported, whether or not the death was related to the research.

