8.2.2 Parental consent

Consistent with our prior studies in this population, we will not require parental consent for study enrollment. Parental consent may decrease participation rates because some youth (17-year-olds) will fear that they may be "outed" as a result of participation. Disclosure of sexual orientation or gender identity may place participating youth at risk for parental harassment, abuse, or expulsion from the home. The nature and scope of the proposed research do not pose more than "minimal risk" to participants, or that "the probability and magnitude of harm or discomfort anticipated in the research are not greater in and of themselves than those ordinarily encountered in daily life or during the performance of routine physical or psychological examinations or tests" (45 CFR Part 46.102). Study measures are standard in this population, as are waivers of parental permission for survey and interview studies.

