8.9 Unexpected and Serious Adverse Event Reporting

A detailed monitoring plan will be included as part of the study protocol, submitted to the IRB, and reviewed and approved by the NIMH before the study begins. Prior to initiation of the study, agreement about the data safety monitoring plan will be confirmed to ensure the safety of subjects and the validity and integrity of the data. The research coordinator at each site will report serious adverse events (SAEs) that are unexpected and study-related immediately to a study physician who will convey this information to the study team, IRB, and the NIH. All AEs and SAEs will be captured, reports will be completed, and information will be entered into the study database. A safety report will detail all serious and unexpected AEs or other unanticipated problems that involve risk to study participants or others and whether these appeared to be related to the study- based interventions or research assessment protocols. All AEs will be reviewed every 6 months, or sooner, with the designated safety Data Safety and Monitoring Board.

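### Section 8.5 sends social impact events to protocol leadership and the IRB without naming the DSMB, so nothing ensures that the board's six-monthly review includes them or that they are counted by arm

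*Combined protocol and SAP*

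**What the plan says.** Section 8.5 treats social impact events as personal problems that result from study participation. Its examples are stigmatization or discrimination, unfair treatment, and that participants "could have problems being accepted by their families and/or communities". Two destinations are given. The routine one is internal: "Social impact events are documented and reviewed on a scheduled basis by the protocol team leadership with the goal of reducing their incidence". The second is the ethics committee or IRB: "Social impact events that are judged by the MPIs/designee to be serious, unexpected, or more severe or frequent than anticipated, will be reported". The DSMB does not appear in the section.

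The safety sections use other terms. Section 7.4.2 states that "SAEs will be defined as death, life threatening illness, hospitalization or prolongation of hospitalization, and persistent/significant disability". Section 7.3.4 gives the DSMB review of SAEs and, more generally, the task to "review endpoints for safety". It keeps the board blinded to allocation unless the board decides otherwise for safety reasons. Section 8.9 adds that "All AEs will be reviewed every 6 months, or sooner, with the designated safety Data Safety and Monitoring Board". None of these sections mentions social impact events, and the documents never define an AE.

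**The concern.** The harms from participation that the protocol describes are mainly social, while the events it explicitly sends to the independent board are labelled AEs and SAEs. The link between the two is missing. If staff treat social impact events as a separate class, which section 8.5 invites, the DSMB could review a report without them.

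The step up from internal review is also weak. It depends on a judgement by the principal investigators or a designee. One of its triggers is a frequency above what was anticipated, and no anticipated frequency is given. With AE undefined, two sites could also record the same event differently, which would make any count hard to interpret.

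The pilot is meant to support a larger efficacy trial. A safety summary limited to AEs and SAEs could carry forward a record that leaves out the harms most particular to this population.

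**Working it through.** The plan has no figure to reproduce here. The check is a trace of every route by which a social impact event could reach the DSMB.

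**Explicit routes.** There are none. Section 8.5 names leadership and the EC/IRB. Section 6.3, on social harm, names child-protection and other agencies and referral resources. Sections 7.3.4, 7.4.1, 7.4.2 and 8.9 do not mention these events.

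**Indirect routes.** There are five.

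1. *Recorded as an AE (8.9).* The DSMB would then see it within 6 months. This requires staff to treat a separately named and separately routed class as an AE, and nothing tells them to.
2. *Listed in the safety report (8.9).* That report covers serious and unexpected AEs and other unanticipated problems that involve risk. Harms already described in the protocol do not fit well under unexpected or unanticipated, and the report's recipient is not stated.
3. *Classed as an SAE (7.4.1, 7.4.2).* The list is death, life-threatening illness, hospitalization and disability, which would not normally include stigma or family rejection. Section 7.4.2 also exempts risks already described in the protocol and consent form from SAE reporting unless they prove more frequent or more serious than expected. Section 7.4.1 anticipates that the DSMB will define study-specific SAEs, but does not say that social harms will be among them.
4. *Added by the DSMB to its own objectives (7.3.4).* This is permitted but not planned.
5. *Picked up by the suggested check for imbalance between arms (7.4.1).* The check names safety and data security, and study drop-out. It does not name social impact events.

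Each route depends on a decision that the text leaves open.

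**Counting by arm.** Under sections 4.5 and 7.2, the arms (40 and 40) differ in app access only in months 0-3. From month 4 the delayed arm has the app too. Months 0-3 are therefore the only period with a concurrent comparison, and no table of social impact events by arm is specified for it.

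**What a count could say (context only).** The plan gives no event rate, so 2% and 5% are assumptions. The chance of at least one event among 40 participants is 1 - (1 - p)^40:

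- p = 0.02: 1 - 0.98^40 = 55%
- p = 0.05: 1 - 0.95^40 = 87%

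With no events in n participants, the one-sided 95% upper bound is 1 - 0.05^(1/n):

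- n = 40: 7.2%
- n = 32 (the 80% retention target, 0.8 × 40): 8.9%

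These figures show what 40 participants per arm can reveal. They do not measure the effect of routing. The bounds also require that every event is ascertained, whereas section 8.5 relies on participants reporting them.

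**The case against.** The strongest reply is that the text is silent and excludes nothing. A reader might infer that the DSMB never sees these events. The documents do not support that. Section 8.9 sends all AEs to the board, and no passage says that a personal problem arising from participation is not an AE. Section 7.3.4 lets the board set report formats and change its objectives, and section 7.4.1 expects it to shape the SAE definition. Section 8.9 also refers to a detailed monitoring plan that NIMH approves before the study begins. All of this stands, and it limits the point to an unassured link.

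Two other strong readings also fail.

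- A reader might infer that only serious events reach the IRB. The trigger in section 8.5 is broader: it also covers unexpected events and those more severe or frequent than anticipated.
- A reader might take section 8.2.2 as describing harm from the app, since it says that "Disclosure of sexual orientation or gender identity may place participating youth at risk for parental harassment, abuse, or expulsion from the home". That passage argues against requiring parental permission. Sections 8.2 and 8.4.1 call the study minimal risk. Section 8.4.2 says only that others may observe a participant using the app.

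Two objections bear on the remedy, and both stand. Only one arm has the app in months 0-3, so a DSMB table labelled exposed versus unexposed, or a listing of each event's relation to app use, would reveal allocation and conflict with the blinding in section 7.3.4. Wait-list participants are also not free of risk, because social impact events follow from participation becoming known and not only from app use.

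**Conclusion.** The point holds as a gap in reporting. Section 8.5 gives social impact events a complete route of their own that does not include the DSMB, and no other section clearly brings them in. Followed as written, the independent board has no assured sight of them, and nothing ensures that they are counted by arm.

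The size is qualitative: no explicit route and five conditional ones. The share of events that would be missed cannot be stated, because it depends on how staff and the DSMB would settle an undefined term. A claim that none would reach the board goes further than the text allows. The conclusion rests on the protocol as given; a separate monitoring plan or DSMB charter could already close the gap. This is a cheap improvement and does not threaten the trial's validity.

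**What to change.** Amend sections 8.5, 8.9 and 7.3.4 as follows.

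- Enter every documented social impact event in the study safety database and include it in the existing six-monthly DSMB report.
- Tabulate events by coded (masked) arm for months 0-3. Show months 4-6 separately and descriptively.
- Hold unmasked arm labels and detail on relation to app use for the final safety report, or for a DSMB decision to unmask under section 7.3.4.
- Report the same counts in the pilot's safety results. Note there that they rest on events participants chose to report, and that wait-list participants also carry the risk that comes with taking part.

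The change affects reporting only and leaves the handling of participants as it is. It uses events that are already documented and a committee that already meets. The cost is a wording amendment, a slightly longer DSMB report and a less favourable-looking safety summary.

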8.6 Benefits

The potential benefits to an individual participant in the study are not known. The potential benefits of the study to others could be considerable. If our hypotheses are true, this study will

make a significant contribution towards improving HIV incidence in YTM. This study has not been designed for the direct benefit of its participants; however, there are a number of ways in which they may derive benefit, such as awareness of HIV status, increased access to HIV prevention tools (e.g., testing, PrEP) and HIV services, if a participant sero-converts. The proposed research will inform the delivery of HIV prevention messages. The knowledge gained will contribute to the body of knowledge regarding the use of health information technology for improving the lives of YTM at risk for HIV. The avoidance of HIV throughout study participation will be a significant personal benefit to participants.

8.7 Participant Privacy and Confidentiality

Access to individually identifiable private information about human subjects. Access to individually identified private information about human subjects will be limited to research team members who collect and manage the data, the Project Director, and the MPIs. De-identified data will be accessible to all members of the research team involved in the data analysis.

Our study team is extremely prudent in keeping subject data secure and confidential. All laboratory specimens, evaluation forms, reports, and other records will be identified by a unique coded number to maintain participant confidentiality. The material, records, and data obtained through participation in the study will be specifically for research purposes. Existing health records may be used with the permission of the participants. Materials will be obtained by trained clinical staff at each study site. Data will be stored using Research Electronic Data Capture (REDCap) at each respective performance site, and then the completely deidentified data will be merged at CUIMC. All laboratory specimens will be identified *only* by the identification number. The code linking the participant identification number to subject identifying information (name, address, etc.) is maintained at the clinical sites through REDCap, and only authorized site personnel have access to the code. Limited individually identifiable private information is collected that is essential for processing participant payments and for analysis purposes.

All study data will be stored in password-protected computers or file cabinets in locked offices. All research team members will pass the protection of human subjects and HIPAA research exams and sign a protocol-specific conflict of interest. Risks will be minimized by not including personal

identifying information on the forms, when possible, and by conducting interviews and collection of personal information in a private setting. All data will be collected using unique patient identification codes. All laboratory specimens, evaluation forms, reports, and other records will be identified by a coded number to maintain participant confidentiality. All records will be stored in a locked file cabinet. Study data from both sites will be collected and managed using REDCap. REDCap is a secure web application designed to support data capture for research studies, providing user-friendly web-based case report forms, real-time data entry validation (e.g., for data types and range checks), audit trails, and a de-identified data export mechanism to common statistical packages (SPSS, SAS, Stata, R/S-Plus). REDCap data collection projects rely on a thorough study-specific data dictionary defined in an iterative self-documenting process by all members of the research team. This iterative development and testing process results in a well-planned data collection strategy for individual studies. REDCap also includes a powerful tool for building and managing online surveys. The research team can create and design surveys in a web browser and engage potential respondents using a variety of notification methods. REDCap is flexible enough to be used for a variety of types of research and provides an intuitive user

interface for database and survey design and data entry. Lastly, clinical information will not be released without written permission of the participant, except as necessary for monitoring by the IRB or the NIH.

8.7.1 Confidentiality of Study Data

We have developed systematic protocols for data handling and storage over multiple cohort studies. To protect the integrity of the participant's data, the RA will assign each participant a unique PID at study enrollment. This code number will be used for all study data. We will maintain a list of participants with links between identifying information and code numbers for the sole purpose of avoiding any duplication in completion of the survey. Only the PIs, RAs, and Project Director will have access to these lists, which will be kept behind double-locks or on a secure server with password protected access. Computer files consist of the tracking database (REDCap), and study data files downloaded from the database. Tracking files are maintained in a highly secure scheduling and monitoring database which both sites can access. This database contains all contact information and is used to schedule and track study visits; it is completely password protected and user access and privileges will be managed by the data manager and Project Director. The tracking database stores contact preferences including information the participant agreed to provide for the purposes of tracking and communication; all communications strictly follow the participants' contact limitations. Data files are exported from REDCap and imported into the SPSS database for storage and analysis. Computer data files never have any identifying information and are encrypted for transfer between study sites. Data files do not include information that could be used to identify the participant from the data file alone. Columbia University will provide a standards-compliant (HIPAA, HHS Cybersecure) private cloud server for the hosting of application content and user data for the duration of the application deployment. This is a secure system and will be further protected by login credentials for limited access to protect participant confidentiality. Participants will also be encouraged to choose a private location to program a password for the application and complete the intervention modules for additional security. They will be prompted to log-out of the website after completing or progressing through any given module.

8.8 Certificate of Confidentiality

This research specifically targets a vulnerable population, children - YTM age 17. We will take every available step to minimize the risk of identifying/linking data being subpoenaed, stolen, or inadvertently released. First, per Section 2012 of the [21st Century Cures Act](#) as implemented in the [2017 NIH Certificates of Confidentiality Policy](#), all ongoing or new research funded by NIH as of December 13, 2016 that is collecting or using identifiable, sensitive information is automatically issued a CoC. As noted on the NIH website, (<http://grants.nih.gov/grants/policy/COC/faqs.htm#187>), a Certificate of Confidentiality will help the research team "...avoid compelled 'involuntary disclosure' (e.g., subpoenas) of names and other identifying information about any individual who participates as a research participant (i.e., about

whom the investigator maintains identifying information) during any time the Certificate is in effect." Second, all research staff members are required to complete ethical clearance certification regarding protection of human's subjects through their relevant IRBs. Third, all studies will have documented procedures to safeguard against the risk of the linking information being stolen by keeping such information in locked spaces to which only essential study personnel who have completed CITI certification for human subjects research ethics training (<http://citiprogram.org>) will have access.

8.9 Unexpected and Serious Adverse Event Reporting

A detailed monitoring plan will be included as part of the study protocol, submitted to the IRB, and reviewed and approved by the NIMH before the study begins. Prior to initiation of the study, agreement about the data safety monitoring plan will be confirmed to ensure the safety of subjects and the validity and integrity of the data. The research coordinator at each site will report serious adverse events (SAEs) that are unexpected and study-related immediately to a study physician who will convey this information to the study team, IRB, and the NIH. All AEs and SAEs will be captured, reports will be completed, and information will be entered into the study database. A safety report will detail all serious and unexpected AEs or other unanticipated problems that involve risk to study participants or others and whether these appeared to be related to the study- based interventions or research assessment protocols. All AEs will be reviewed every 6 months, or sooner, with the designated safety Data Safety and Monitoring Board.

